## 12.1.1 Pre-Surgery screening Visit (Day -45 to Day -1)

Below is a list of study procedures to be undertaken at Pre-Surgery Visit (Screening). The procedures must be performed in the order presented below unless otherwise stated. All ocular assessments must be done monocularly.

For applicable assessments, both eyes must qualify for the study, therefore the screening assessments will be performed in both eyes.

Upon signing the informed consent, subjects are considered enrolled. The subject is assigned a single subject identifier at the Pre-Surgery Visit. The subject identifier consists of a combination of a 4 digit investigator number and a 5 digit subject number. The number is automatically generated sequentially by the EDC system. As an example: "4584.00001" (The investigator number and subject number are separated by a "." character).

This number is used throughout the clinical study. Within 45 business days of surgery, subjects will be screened and randomized based on 1:1 allocation to receive EX500 for Topography Guided LASIK or VisuMax for SMILE.

1. Upon identification of a possible study participant, carry out the informed consent process. Refer to Section 16.2 Informed Consent Procedures.

*NOTE*: Subjects must formally consent to participate in the study prior to undergoing any study specific testing. Upon signing informed consent, subjects are considered enrolled in

Alcon - Business Use Only Protocol - Clinical Effective Date: 19-Mar-2017
Page 54 of 81

Document: TDOC-0052425 Version: 2.0; Most-Recent; Effective; CURRENT

Status: Effective

the study.

2. Perform a urine pregnancy test if the subject is a woman of childbearing potential.

- 3. Document demographics, ocular and non-ocular medical history, ocular and non-ocular concomitant medications.
- 4. Administer the RSVP Questionnaire (a 52-item questionnaire) to assess quality of vision and vision related quality of life.
- 5. Administer the SQDES to evaluate dry eye symptom and severity.

*NOTE:* Investigators and site staff must review both questionnaires results prior to subjects leaving the office to ensure completeness.

6. Conduct the following procedures in an order that is feasible for your site:

### NOTES:

- Each subject must be refracted by an ophthalmologist, optometrist, or a skilled technician. For further details, refer to MOP.
- To ensure the stability of refraction, eligible subjects who currently wear contact lenses must discontinue their use for the appropriate amount of time before undergoing refractive laser surgery in the study as indicated in Table 12–1.

*NOTE*: A contact lens wearer is defined as someone who has worn contact lenses within 3 months prior to the Pre-Surgery Visit.

Table 12–1 Minimum time to stop wearing contact lens before Pre-Surgery Visit

Type of Contact Lens	Minimum Time to Stop Wearing Contact Lens before Pre-Surgery Visit
Hard (PMMA) lenses	3 weeks
RGP lenses	2 weeks
Soft (extended and daily wear)	3 days

- Perform lighting measurements for VA and contrast sensitivity testing.
- Measure distance UCVA in photopic conditions using an Early Treatment
  Diabetic Retinopathy Study (ETDRS) chart at 3 meters (10 feet) or 4 meters (13
  feet) recorded in logMAR. For subjects who cannot read English letters, a
  numerical, Tumbling E or a Landolt C logMAR chart can be used.
- Measure uncorrected contrast sensitivity in mesopic conditions using a Vector

Effective Date: 19-Mar-2017 Page 55 of 81 Alcon - Business Use Only Protocol - Clinical

Version: 2.0; Most-Recent; Effective; CURRENT Document: TDOC-0052425

Status: Effective

Vision Chart, recorded in logCS.

Measure manifest refraction at 4 meters and adjust for optical infinity.

- Measure distance BCVA in photopic conditions using Early Treatment ETDRS chart at 3 meters (10 feet) or 4 meters (13 feet) recorded in logMAR. For subjects who cannot read English letters, a numerical, Tumbling E or a Landolt C logMAR chart can be used.
- 7. Conduct the following procedures in an order that is feasible for your site:
  - Perform keratometry using a Topolyzer Vario.
  - Perform topography using a Topolyzer Vario. Verify that the corneal astigmatism is regular (bow-tie shape).
  - Perform pupillometry under mesopic conditions using an infrared pupilometer. The same instrument should be used throughout the study.
  - Perform axial length measurement using an optical biometer or any other instrument. The same instrument should be used throughout the study.
  - Perform pachymetry using an ultrasonic contact pachymeter device or any other instrument. The same instrument should be used throughout the study.

- 8. Perform slit lamp examination.
- 9. Measure IOP using a Goldmann tonometer or any other instrument. The same instrument will be used throughout the study.
- 10. Perform cycloplegic refraction using a phoropter and adjust for optical infinity. The same equipment should be used throughout the study.
- 11. Perform dilated fundus examination.
- 12. Record any AEs. Refer to Section 13 for further details.
  - *NOTE:* SAEs must be entered into EDC within 24 hours of the Investigator's knowledge.
- 13. Evaluate subject against all entry criteria. Document the subject status.
- 14. Randomize the subject and schedule the Surgery Visit to occur within 45 days of the Pre-

Effective Date: 19-Mar-2017 Page 56 of 81 Alcon - Business Use Only Protocol - Clinical

Version: 2.0; Most-Recent; Effective; CURRENT Document: TDOC-0052425

Status: Effective

Surgery Visit (Screening).

*NOTE:* The subject should be discontinued from participation in the study if:

Any complication occurred prior to any laser coming in contact with the eye.

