### 9.2.1 **Procedures Per Study Visit**

The clinical study procedures to be conducted at each study visit are listed in Table 6–1 and detailed in Section 12. Further details on the actual assessments are provided in full in the Manual of Procedures (MOP) for this study. A brief summary of the procedures performed by visit is provided here.

*NOTE*: All assessments performed at the eye level as listed in Table 6–1 will be done monocularly.

At the Pre-Surgery Visit (Day -45 to Day -1) the subject will sign the informed consent form (ICF). Standard procedures will be performed to determine subject eligibility. The subject will be evaluated against all entry criteria. The subject status (e.g., continuing or screen failure) will be documented and the subject's data will be entered into electronic data capture (EDC) at the time of consent to assign subject number. For continuing subjects:

- 1. The subject will be randomized to Topography Guided LASIK or SMILE in the EDC system.
- 2. The subject will be provided with pre-surgery information and medications in accordance with investigational site's standard of care.
- 3. The Investigator will consider any unresolved complications or events in either eye prior to surgery.
- 4. The Surgery Visit (Day 0) will be scheduled to occur within 45 calendar days of the Pre-Surgery Visit (Screening).

Print Date: Printed By:

Effective Date: 19-Mar-2017 Page 43 of 81 Alcon - Business Use Only Protocol - Clinical

Version: 2.0; Most-Recent; Effective; CURRENT Document: TDOC-0052425

Status: Effective

a. Inclusion/ exclusion criteria will be reviewed prior to surgery to ensure subjects are still eligible for the study (see Section 10.1 and 10.2). Subjects failing to pass entry criteria will not be re-screened. If a subject is excluded post-randomization and prior to the laser touching the eye (defined as once flap creation is initiated for LASIK and once laser touches the eye for SMILE), the subject should be discontinued from participation in the study.

- b. The surgery will be performed on both eyes. The subject will be prepared for surgery in accordance with site specific operating procedures.
- 5. After surgery, the ocular and/or non-ocular concomitant medication will be administered as per Investigator's standard procedures.

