#### 9.3 Risk Benefit Assessment

#### 9.3.1 **Potential Risks**

### LASIK and SMILE

The risks of LASIK are well known, however, the risks of SMILE are still being investigated because it is a newer procedure (Sekundo 2011, Solomon 2009).

Some risks are similar for LASIK and SMILE. First, the laser could malfunction and the procedure would need to be stopped before completion. If this happens, a second surgical procedure may be needed. Second, LASIK and SMILE may not fully correct, or may overcorrect the refractive error, leaving the subject with some residual refractive error.

Alcon - Business Use Only Protocol - Clinical Effective Date: 19-Mar-2017
Page 44 of 81

Document: TDOC-0052425 Version: 2.0; Most-Recent; Effective; CURRENT

Status: Effective

Undercorrection or overcorrection may be treatable by performing a second refractive surgery. Additionally, decentration of the treatment as a result of off-center placement of the laser may occur, which could affect the outcome and consequently the subject's vision.

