### **SMILE**

Ivarsen et al (Ivarsen 2014) performed a study to evaluate the safety of SMILE. A total of 1574 eyes were treated with SMILE and followed for 3 months. In this study, the pre-surgery complications reported in at least one eye were as follows:

- Abrasion at the incision
- Lenticule extraction difficulties
- Minor tear at the incision
- Suction loss
- Central abrasion
- Cap perforation
- Major tear

Effective Date: 19-Mar-2017 Page 45 of 81 Alcon - Business Use Only Protocol - Clinical

Version: 2.0; Most-Recent; Effective; CURRENT Document: TDOC-0052425

Status: Effective

Impossible lenticule extraction

The post-surgery complications reported in at least one eye were as follows:

- Haze
- Dry surface
- Epithelial islands at incision
- Fiber in the interface
- Infiltrates/keratitis
- Monocular ghost images
- Interface inflammation

In general, these complications may be minimized by sufficient proficiency in performing the SMILE procedure, and laser setting optimization.

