## 11 TREATMENT

The treatment in this study involves the use of either the EX500 for Topography Guided LASIK or the VisuMax for SMILE as described in Table 11–1.

For the purposes of this study, treatment will be considered to have begun once the flap creation is initiated for LASIK and once the laser touches the eye for SMILE.

Alcon - Business Use Only Protocol - Clinical Effective Date: 19-Mar-2017 Page 49 of 81

Document: TDOC-0052425 Version: 2.0; Most-Recent; Effective; CURRENT

Status: Effective

Table 11–1 Treatments

	Test Article: Wavelight EX500 for Topography Guided LASIK	Control Article: Zeiss VisuMax for SMILE
Administration	The EX500 laser is used to ablate the corneal stroma which results in the refractive error correction. Prior to ablation, the corneal flap may be created with a femtosecond laser or microkeratome blade at the surgeon's discretion.  Treatment planning will be based on topography.	The VisuMax Laser keratome is used to create a lenticule in the corneal stroma and a channel for the removal of the lenticule. Removal of the lenticule results in the refractive error correction.
Duration of treatment	The treatment is intended to last the subject's lifetime.	The treatment is intended to last the subject's lifetime.

The Investigator will be responsible for ensuring that the EX500 and VisuMax Laser Systems are used in accordance with their indications and procedural guidance provided in their respective Operator's (or User's) and Procedure's Manuals by a licensed ophthalmologist with LASIK and/or SMILE surgery experience. A summary of the necessary training and experience needed to use the investigational device must be recorded at the site.

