### 12.1.2 **Surgery Visit (Day 0)**

Prior to surgery, the Investigator must ensure that the treatment planning has been completed and that the subject is still qualified.

If a subject is excluded post-randomization and prior to the Surgery Visit (i.e. the laser does not come in contact with the eye), the subject must be discontinued from participation in the study. Refer to Section 12.4 for further details.

During the day of surgery, the Investigator must record information regarding the surgery and related conditions and also details regarding medication used during the surgery, any problems or complications or other procedures that occur during the surgery.

Below is a list of procedures to be undertaken at Surgery Visit. Procedures must be performed in the order presented below unless otherwise stated. All ocular assessments will be done monocularly.

Activities involving multiple delegated staff members may be performed in parallel if this aligns with the study specified sequence.

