#### 12.4 **Discontinued Subjects**

Discontinued subjects are those who withdraw, or are withdrawn from the study after signing the ICF and prior to completing all study visits. Subjects signing consent, but withdraw or are withdrawn prior to randomization will be considered discontinued due to screen failure, and the failed entry criterion must documented in source document and EDC (refer to Section 10).

Subjects may discontinue study participation at any time and for any reason. Subjects who complete the laser treatment in either eye will not be discontinued by the Investigator.

Subject numbers from discontinued subjects will not be reissued. Discontinued subjects will not be replaced.

It is the Investigator's responsibility to select only those subjects who are likely to be both willing and able to complete the required follow-up for participation in this study.

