# **15.2** Analysis Data Sets

The following analysis sets will be defined for this study: intention to treat (ITT) and safety analysis set. Assignment of study eyes to the appropriate analysis set(s) will be determined prior to DBL.

The ITT analysis set will contain all study eyes for which study treatment has begun for the set of subjects that are randomized. For the purposes of this study, the treatment will be considered to have begun once the flap creation is initiated for LASIK and once laser touches the eye for SMILE.

All eyes in the ITT analysis set will be assigned to the treatment to which they are randomized.

The safety analysis set will contain all study eyes for which study treatment has begun; all eyes in the safety analysis set will be assigned to the treatment actually received. In general, the ITT analysis set will be used to display subject disposition, demographics and baseline characteristics, medical history and the analysis of the effectiveness endpoints. The safety analysis set will be used for the analysis of the safety endpoints.

Alcon - Business Use Only Protocol - Clinical Effective Date: 19-Mar-2017 Page 70 of 81

Document: TDOC-0052425 Version: 2.0; Most-Recent; Effective; CURRENT

Status: Effective

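### The discontinuation rules do not match the start of treatment that defines ITT, so a begun-but-abandoned eye can lack a Month 3 value (minor)

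*Protocol*

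**What the plan says.** **Start of treatment and ITT.** Protocol Sections 11 and 15.2 and SAP Section 3 agree. Treatment has begun "once the flap creation is initiated for LASIK and once laser touches the eye for SMILE", and every such eye of a randomized subject is in the ITT set. Protocol 9.2.1 uses the same point as its cut-off for removing a randomized subject: "defined as once flap creation is initiated for LASIK and once laser touches the eye for SMILE". Table 11-1 adds that "the corneal flap may be created with a femtosecond laser or microkeratome blade", so LASIK treatment can begin with no laser on the eye.

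**Discontinuation.** Three places in Section 12 use other cut-offs.

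- 12.1.1, note under step 14: the subject should be discontinued if "Any complication occurred prior to any laser coming in contact with the eye".
- 12.1.2, on subjects excluded after randomization: "prior to the Surgery Visit (i.e. the laser does not come in contact with the eye), the subject must be discontinued".
- 12.4: "Subjects who complete the laser treatment in either eye will not be discontinued by the Investigator".

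**Unfinished procedures.** Protocol 9.3.1 foresees these for both arms: "First, the laser could malfunction and the procedure would need to be stopped before completion". For SMILE it also lists suction loss and "Impossible lenticule extraction" among complications reported in at least one eye of a published series.

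**Analysis.** Protocol 15.5 and SAP 5.5 analyse effectiveness on observed data without imputation. Neither document says how an abandoned eye is scored.

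**The concern.** An ITT set is useful only if its members are followed to the endpoint. Here the set is fixed when treatment begins, while protection from investigator discontinuation in 12.4 starts only when laser treatment is completed. Eyes that fall between the two points are those in which surgery went wrong. Inclusion criterion 4 requires at least 0.75 D of manifest cylinder, so an eye left uncorrected would probably miss the 0.5 D threshold. Its absence from the analysis would then be related to outcome, unlike ordinary dropout. At stake is the removal of some likely failures from the primary comparison, by a route that the text leaves open.

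**Working it through.** **1. Setting the rules side by side**

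| Rule | Cut-off | Agrees with Section 11? |
|---|---|---|
| 9.2.1 | Flap initiation / laser touch | Yes |
| 12.1.1 note | Contact by any laser | Yes for SMILE and for a femtosecond flap; no for a blade flap |
| 12.1.2 | Contact by the laser | Yes for SMILE; no for a blade flap, nor for any LASIK flap if the laser meant is the excimer |
| 12.4 | Laser treatment completed in at least one eye | No, in either arm |

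The conflict in 12.1.1 and 12.1.2 is thus confined to LASIK. The gap in 12.4 covers both arms, but only subjects in whom treatment began and neither eye was completed.

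**2. From exit to a missing value**

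Table 6-1, note k, has an exiting subject undergo the Month 12 procedures at the last available visit. That visit need not fall in the Month 3 window (Day 70 to 98). With no imputation, the eye contributes nothing to the primary test.

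**3. The plan's own figure**

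Inputs (Protocol 15.9): 90% v 80%, correlation between eyes 0.39, two-sided 5%, 90% power. The pooled two-proportion formula gives 266 eyes per arm. The design effect is 1 + (2 - 1) × 0.39 = 1.39. Then 266 × 1.39 = 369.7 eyes, or 184.9 subjects, so 185. Power at 370 eyes per arm is 90.0%. The plan's figure is reproduced.

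**4. Scale of a loss**

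The documents give no abandonment rate. As an assumption, let 0 to 2 eyes per arm be lost from the 400 begun (200 subjects × 2), and let every lost eye be a failure, which is the worst case. The observed rate in an arm is p / (1 - f), with f = eyes lost / 400.

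- One eye, p = 0.80: 0.80 / 0.9975 = 0.8020, a rise of 0.20 points.
- One eye, p = 0.90: 0.90 / 0.9975 = 0.9023, a rise of 0.23 points.

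Now suppose no true difference, with 370 / 1.39 = 266.2 effective eyes per arm. The standard error of the difference is √(2 × 0.80 × 0.20 / 266.2) = 3.47 points at 80%, and 2.60 points at 90%. The chance of a significant result in favour of LASIK (nominal 2.5%) is:

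| Lost (LASIK, SMILE) | Shift at 80% | Chance | Shift at 90% | Chance |
|---|---|---|---|---|
| (2, 0) | +0.40 | 3.26% | +0.45 | 3.72% |
| (1, 0) | +0.20 | 2.86% | +0.23 | 3.05% |
| (1, 1) or (2, 2) | 0.00 | 2.50% | 0.00 | 2.50% |
| (0, 1) | -0.20 | 2.18% | -0.23 | 2.03% |
| (0, 2) | -0.40 | 1.89% | -0.45 | 1.64% |

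At the planned 90% v 80%, the observed difference would be 10.45 points for (2, 0), 10.05 for (2, 2) and 9.60 for (0, 2). For comparison, the planned 7% post-surgery dropout is 0.07 × 400 = 28 eyes per arm.

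**The case against.** The case for leaving the text alone is substantial.

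- **Context.** The 12.1.1 note belongs to the screening visit, and 12.1.2 speaks of exclusion before the Surgery Visit. Neither is written for an eye abandoned during surgery, and 9.2.1 shows the intended cut-off. A reader might infer a deliberate rule that removes failed LASIK eyes and favours the sponsor's device. The documents do not support that; this part is a wording inconsistency.
- **12.4 permits and does not direct.** It says who will not be discontinued. A reader might infer that everyone else must be. Nothing says so, and the default points to follow-up: effectiveness assessments at all post-surgery visits (9.2.1), diligence in rescheduling (12.3), and efforts to prevent missed visits (14.2). A subject with one abandoned and one completed eye stays protected.
- **Failure is not certain.** Section 9.3.1 describes flap complications as infrequent and managed during surgery, possibly by conversion to PRK, and says a stopped procedure may need a second one. Such an eye could be within 0.5 D at Month 3.
- **Unseen detail.** Section 12.1.2 refers to MOP Table 4-1 for subjects not treated bilaterally as planned. It is not among the documents and may cover some of this.

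All four points stand, and they limit the concern to a minor one. They do not remove it. Section 9.2.1 does not cure the word *complete* in 12.4, general encouragement to keep visits is weaker than a rule, and recording surgical problems (12.1.2, SAP 6.3.8) does not supply a Month 3 cylinder.

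**Conclusion.** The mismatch is real and minor. For LASIK only, the laser-contact wording in 12.1.1 and 12.1.2 conflicts with the start of treatment. In either arm, 12.4 leaves unprotected a subject in whom treatment began but was completed in neither eye; that subject may, not must, be exited before Month 3, and the ITT eyes then drop out of the observed-data analysis.

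The number of such eyes, and the direction and size of any bias, cannot be derived from the documents. The effect is probably small. A reader might take the 3.7% in the table as the trial's type I error. It is not: it needs two LASIK losses, no SMILE losses, both eyes certain failures, and 90% true success in both arms, and none of the loss assumptions has a source in the documents. Equal losses give the nominal 2.5%, and more SMILE losses give less. The sample size and power are not in question.

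**What to change.** 1. In 12.1.1 and 12.1.2, replace the laser-contact wording with *before study treatment has begun, as defined in Section 11*, which is the cut-off that 9.2.1 already uses.
2. In 12.4, extend the protection from subjects who complete laser treatment to subjects *in whom study treatment has begun in either eye*, for both arms.
3. Require Month 3 manifest refraction for every ITT eye, including abandoned or converted eyes, unless the subject withdraws consent.

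The cost is three edited sentences, one added requirement and probably a few extra Month 3 visits. The sample size does not change. This does not recover subjects who withdraw, and it does not say how an eye converted to another procedure should be scored; those remain questions for the missing-data section of the SAP.

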### 12.1.2 **Surgery Visit (Day 0)**

Prior to surgery, the Investigator must ensure that the treatment planning has been completed and that the subject is still qualified.

If a subject is excluded post-randomization and prior to the Surgery Visit (i.e. the laser does not come in contact with the eye), the subject must be discontinued from participation in the study. Refer to Section 12.4 for further details.

During the day of surgery, the Investigator must record information regarding the surgery and related conditions and also details regarding medication used during the surgery, any problems or complications or other procedures that occur during the surgery.

Below is a list of procedures to be undertaken at Surgery Visit. Procedures must be performed in the order presented below unless otherwise stated. All ocular assessments will be done monocularly.

Activities involving multiple delegated staff members may be performed in parallel if this aligns with the study specified sequence.

